#### 5.6.6 Exploratory Analysis

5.6.6.1 Two new variables will be defined and all comparative analyses that were done for the primary analysis above will be repeated for these two new variables:

5.6.6.1.1 The number of grade  $\geq 2$  lesions

5.6.6.1.2 An adjusted number of lesions weighted by grade. The weighted grade will be computed as follows: (Number of grade I lesions) + (2  $\times$  Number of grade II lesions) + (3  $\times$  Number of grade III lesions).

5.6.6.2 Comparative analysis of the decrease in number of grade  $\geq 2$  lesions will be applied on a sub-group of subjects with at least one grade  $\geq 2$  lesion at baseline.

5.6.6.3 Figures displaying the reduction in number of grade  $\geq 2$  lesions and the reduction of adjusted number of lesions weighted by grade from Baseline to Day 56 will be generated.

	DOCUMENT NUMBER: 029-BST-PLN-001	PAGE: 32 of 45
TITLE: Statistical Analysis Plan for study:  A Phase 2 Randomized, Double-Blind, Placebo-Controlled, Parallel-Cohort Study to Evaluate the Efficacy, Safety, Tolerability, and Pharmacokinetics of Once-Daily Application of Topical VDA-1102 Ointment for 28 Days in Subjects with Actinic Keratosis	EFFECTIVE DATE : 22/MAY/2017 REVISION NUMBER : 2.0	

5.6.6.4 Chi-square test or Fisher's exact test (as is appropriate) will be used for analyzing the difference in percent of subjects with complete clearance of study AK lesions at Day 56 between each of the active groups versus the placebo group. Logistic regression will be applied for analyzing the difference in proportions of complete clearance with adjustment for site and for other covariates suspected as affecting the outcome and which will be found different between the treatment groups.

5.6.6.5 All analyses mentioned above on complete clearance will be performed on  $\geq 75\%$  clearance,  $\geq 50\%$  clearance and  $\geq$  overall median% clearance as well.

5.6.6.6 Analyses mentioned above on complete clearance will be performed on clearance of grade  $\geq 2$  lesions as well.

5.6.6.7 The within-group decrease in number of AK lesions from baseline to each visit will be analyzed using paired t-test or signed rank test for two means (paired observations, as is appropriate) on the Day 84 completers subgroup.

5.6.6.8 Comparative analysis of the decrease in number of AK lesions from baseline to day 84 will be applied between each of the active groups versus the placebo group using the two-sample t-test, the non-parametric Wilcoxon-Mann-Whitney rank sum test for independent samples, or the Median test (as appropriate).

5.6.6.9 The effect of compliance (e.g. days dosed and tube weight) on the primary endpoint will be tested by sensitivity analysis. If the effect of compliance will be found significant, two additional analyses will be performed:

5.6.6.9.1 Analysis of Covariance (ANCOVA) will be applied in order to test the differences in change in number of AK lesions between the treatment groups adjusted for subject compliance. This analysis is included in primary analysis (see 5.6.3.2)

5.6.6.9.2 A relevant compliance cutoff will be computed and a stratified analysis will be performed according to this cutoff.

	DOCUMENT NUMBER: 029-BST-PLN-001	PAGE: 33 of 45
TITLE: Statistical Analysis Plan for study: A Phase 2 Randomized, Double-Blind, Placebo-Controlled, Parallel-Cohort Study to Evaluate the Efficacy, Safety, Tolerability, and Pharmacokinetics of Once-Daily Application of Topical VDA-1102 Ointment for 28 Days in Subjects with Actinic Keratosis	EFFECTIVE DATE : 22/MAY/2017 REVISION NUMBER : 2.0	

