5.6.3 Disposition of subjects (Table 14.1-1 – 14.1-2)

5.6.3.1 The number of subjects that randomized into the study, the number of subjects in the ITT, mITT and PK populations, and the number of study completers will be presented.

5.6.3.2 The reasons for early termination/ withdrawal and any randomization errors will be summarized.

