## 5.6.5 Efficacy Primary Analysis

- 5.6.5.1 The efficacy analysis will be performed with the ITT, mITT and PP populations (see Tables 14.2-1 - 14.2-9). The primary efficacy endpoint is the decrease from baseline in number of AK lesions. The within-group decrease in number of AK lesions from baseline to each visit will be analyzed using paired t-test or signed rank test for two means (paired observations, as is appropriate).
- 5.6.5.2 Comparative analysis of the decrease at Day 56 (mentioned above) will be applied between each of the active groups versus the placebo group using the two-sample t-test, the non-parametric Wilcoxon-Mann-Whitney rank sum test for independent samples, or the Median test (as appropriate) and using the Analysis of Covariance (ANCOVA), after optionally ranking transformation of the variable, with adjustment for sites and for other covariates suspected as affecting the outcome and which will be found different between the treatment groups.
- 5.6.5.3 Figures depicting the number of lesions by visit and by treatment group and depicting the reduction in number of lesions from Baseline to Day 56 will be generated
- 5.6.5.4 Binary variable will be defined based on the decrease in number of AK lesions at Day 56 according to a relevant cutoff (first quartile, median, third quartile or other cutoff computed by ROC curve sensitivity analysis). Comparative analysis of this variable will be applied between each of the active groups versus the placebo group using Chi-square test or Fisher's Exact test and using logistic regression with adjustment for site and for other covariates suspected as affecting the outcome and which will be found different between the treatment groups.

	DOCUMENT NUMBER: 029-BST-PLN-001	PAGE: 31 of 45
TITLE: Statistical Analysis Plan for study:  A Phase 2 Randomized, Double-Blind, Placebo-Controlled, Parallel-Cohort Study to Evaluate the Efficacy, Safety, Tolerability, and Pharmacokinetics of Once-Daily Application of Topical VDA-1102 Ointment for 28 Days in Subjects with Actinic Keratosis	EFFECTIVE DATE : 22/MAY/2017 REVISION NUMBER : 2.0	

5.6.5.5 If the two active VDA-1102 groups trend similarly then these two groups may be pooled and compared to the placebo group in order to achieve higher statistical power.

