5.6.5.6 The overall effect and trend of differences in the decrease over time between the groups will be analyzed using a mixed-effect model for repeated measures. The model will include decrease from baseline at any time, the fixed effect time, and the interaction of treatment and time. Contrast will be calculated for each time point (Days 7, 14, 28 and 56) versus baseline and the overall effect. The model will be adjusted for site and for other covariates suspected as affecting the outcome and which will be found different between the treatment groups.

5.6.5.7 For the ANCOVA analysis, logistic regression and mixed-effect model for repeated measures detailed above, if necessary, grouping of sites will be done based on similarities and differences observed between sites by post-hoc contrasts of ANOVA.

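### The SAP places a compliance-adjusted ANCOVA in the primary analysis, and its covariate rule does not keep post-randomisation variables out

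*SAP*

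**What the plan says.** SAP 5.6.6.9, under Exploratory Analysis, tests whether compliance (days dosed and tube weight are the examples given) affects the primary endpoint. It continues: "If the effect of compliance will be found significant, two additional analyses will be performed". No test or level is given for that trigger. The first of the two analyses, 5.6.6.9.1, is an ANCOVA of the "differences in change in number of AK lesions between the treatment groups adjusted for subject compliance. This analysis is included in primary analysis", with a pointer to 5.6.3.2. That item reads: "The reasons for early termination/ withdrawal and any randomization errors will be summarized".

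The only ANCOVA under Efficacy Primary Analysis is in 5.6.5.2. Day 56 is to be compared by t-test, Wilcoxon-Mann-Whitney test, "or the Median test (as appropriate) and using the Analysis of Covariance (ANCOVA"), adjusted for site and "for other covariates suspected as affecting the outcome and which will be found different between the treatment groups". Nothing there restricts covariates to baseline variables. The same open rule governs three other models:

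- 5.6.5.4: "using logistic regression with adjustment for site and for other covariates suspected as affecting the outcome"
- 5.6.5.6: "The model will be adjusted for site and for other covariates suspected as affecting the outcome"
- 5.6.6.4: "difference in proportions of complete clearance with adjustment for site and for other covariates suspected as affecting the outcome"

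Under protocol 13.7, compliance is recorded during treatment, by tube weights at Days 7, 14 and 28, a dosing diary and weekly contact. Protocol 7.6 lets the investigator interrupt or space out dosing. SAP 5.6.1.2 says the SAP overrides the protocol on data handling and analysis.

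**The concern.** The compliance-adjusted ANCOVA is exploratory by placement and primary by its own sentence. Correcting the pointer to 5.6.5.2 would not solve this, because the covariate rule there admits compliance whenever it is suspected of affecting the outcome and differs between arms. An arm difference in compliance is the condition under which adjusting for it can mislead.

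Compliance follows randomisation. If treatment changes it, and some patient characteristic drives both compliance and lesion response, conditioning on it breaks the comparability that randomisation provides. The adjusted comparison can then show an effect where there is none, or shrink a real one. If treatment leaves compliance unchanged, the adjustment adds no bias.

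**Working it through.** **The plan's own figure.** With effect size 0.83, two-sided 0.045 and a two-group t-test, the noncentral t gives 79.0% power at 24 per arm and 80.7% at 25. So 25 per arm is right for 80%. Recruitment: 75 / 0.9 = 83.3, rounded up to 84. Alpha: 0.005 + 0.045 = 0.05. The sizing rests on the unadjusted test.

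**Model for the adjusted comparison (null case).** Let T be the arm (0 or 1) and U an unmeasured patient factor.

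- Compliance: C = √l·U − k·T + error
- Outcome (lesion decrease): Y = √l·U + error, with no treatment effect
- Within-arm variances are 1. k is the arm difference in compliance in SD units. l is the share of variance due to U.

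Within arm, cov(C, Y) = l and var(C) = 1, so the slope of Y on C is l. The adjusted arm coefficient is 0 − l × (−k) = k × l, although the true effect is 0. Example: k = 0.5, l = 0.5 gives 0.25 SD.

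**Inputs.** 25 per arm and alpha 0.045 come from SAP 5.3.2. The documents give neither k nor l, so ranges are shown. Both trigger levels are assumed to be p < 0.05. Each cell has 40,000 null trials (Monte Carlo SE √(0.045 × 0.955 / 40,000) ≈ 0.001).

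- Route A (5.6.6.9.1): the adjusted p-value is used if the compliance coefficient is significant, otherwise the t-test.
- Route B (5.6.5.2): the adjusted p-value is used if compliance differs significantly between arms, otherwise the t-test.

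Each cell shows l = 0.1 / 0.3 / 0.5.

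| k | Bias k × l (SD) | Type I error, route A (%) | Type I error, route B (%) |
|---|---|---|---|
| 0 | 0 / 0 / 0 | 4.8 / 4.8 / 4.6 | 4.5 / 4.2 / 3.9 |
| 0.2 | 0.02 / 0.06 / 0.10 | 4.8 / 5.3 / 6.2 | 4.5 / 4.4 / 4.1 |
| 0.5 | 0.05 / 0.15 / 0.25 | 5.2 / 7.3 / 15.0 | 4.8 / 5.3 / 8.2 |
| 1.0 | 0.10 / 0.30 / 0.50 | 5.8 / 14.6 / 40.8 | 5.3 / 14.5 / 38.4 |

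The unadjusted t-test rejects in 4.3% to 4.7% of trials in every cell. Route A's trigger fires in 10% / 56% / 96% of trials for l = 0.1 / 0.3 / 0.5. Route B's fires in 5%, 10–11%, 41% and 93% for k = 0, 0.2, 0.5 and 1.0.

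**Days dosed has a ceiling.** With C replaced by min(28, round(28 + 3C)), the largest values are:

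- k = 0.5: 10.3% (A) and 5.7% (B)
- k = 1.0: 28.6% (A) and 26.0% (B)

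**Cross-check with other inputs** (6,000 runs per scenario). Compliance is 0.5 to 0.8 SD lower on active, and its within-arm correlation with outcome is 0.3 to 0.5. Under the null, the adjusted test rejects in 7.8% to 29.8% of runs with a spurious effect of 0.15 to 0.40 SD. The unadjusted test rejects in 4.0% to 5.0%. With no arm difference in compliance, the adjusted test rejects in 4.5% to 4.8%.

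**Direction.** The sign follows the arm difference in compliance. If compliance were higher on active, the bias would be −k × l. At k = 0.5, l = 0.5, a true effect of 0.83 SD would be estimated as 0.83 − 0.25 = 0.58 SD.

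**The case against.** **It is a drafting slip.** The item sits under an exploratory heading, is conditional, follows from a sensitivity analysis and carries a wrong section number. The sentence may only mean that the ANCOVA method is described elsewhere. That is plausible. However, Appendix I lists one ANCOVA table (14.2-19) and none titled as compliance-adjusted, which fits the reading that compliance goes into the primary model.

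**The error rates assume that the adjusted result replaces the t-test.** SAP 5.6.5.2 runs both, and only the t-test carries the 0.045 level and the sample size. It is fair that no replacement rule is written, but the inflation does not depend on one. At l = 0.5, the adjusted test alone rejects in 14.9% of null trials at k = 0.5 and 40.4% at k = 1.0. Counting a success on either test gives 16.8% and 42.5%. The SAP does not say which test decides.

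**The inputs are assumed and the large values are unlikely.** This stands. At k = 0.2 the worst case is 6.2% by route A, and route B shows no inflation. Protocol 5.3 expects neither necrosis nor inflammation from the drug, so nothing in the documents predicts a 1 SD arm difference. Protocol Table 1 does record slight local effects in minipigs at the 10% strength, and SAP 5.6.7.5 plans to summarise drug holidays and dosing adjustments by arm, so a modest difference is possible.

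**The fix is too wide.** No text brings compliance by name into the logistic or repeated-measures models, and complete clearance (5.6.6.4) is exploratory anyway. It is true that those edits resolve no explicit contradiction. They close the same open rule, and 5.6.5.4 and 5.6.5.6 are in the primary section. The 5.6.6.4 edit is for consistency.

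**Conclusion.** The concern holds. The SAP says the compliance-adjusted ANCOVA belongs to the primary analysis, its pointer leads to an unrelated section, and the only primary ANCOVA has a covariate rule that can admit compliance. The textual finding is certain. The consequence depends on k and l, which are unknown:

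- no bias if treatment does not affect compliance;
- little or no inflation at a 0.2 SD arm difference;
- 5.2% to 15.0% (route A) or 4.8% to 8.2% (route B) at 0.5 SD, with lower maxima if days dosed is capped;
- up to about 41% only in the upper corner, k = 1.0 and l = 0.5.

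The unadjusted comparison that sized the trial is unaffected. This should be corrected, but it does not invalidate the design.

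**What to change.** 1. In SAP 5.6.6.9.1, replace the sentence assigning the analysis to the primary analysis, and its reference to 5.6.3.2, with a statement that the analysis is exploratory.
2. In 5.6.5.2, 5.6.5.4, 5.6.5.6 and 5.6.6.4, state that covariates are limited to variables measured before the first dose.
3. Keep the compliance-adjusted and compliance-stratified analyses as exploratory output, not used for the between-arm conclusion.

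The cost is five short text edits. No data are added, no planned analysis is lost, and the sample size and power do not change.

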### 5.6.7 Safety analysis

- 5.6.7.1 All safety data will be summarized for the ITT population.
- 5.6.7.2 Adverse events will be coded according to coding dictionaries (MedDRA version 19.1 or higher) and presented in tables by System Organ Class (SOC) and Preferred Term (PT) and by treatment group.
- 5.6.7.3 Secondary analysis
  - 5.6.7.3.1 The within-group changes from baseline to each visit in the Composite Local Skin Reaction score and in all of its components will be analyzed using Paired t-test or Signed- rank test for two means (paired observations, as is appropriate).
  - 5.6.7.3.2 The within-group changes from baseline to each visit in the Composite Local Skin Reaction score and in all of its components will be analyzed using Paired t-test or Signed- rank test for two means (paired observations, as is appropriate) on the Day 84 completers subgroup.
  - 5.6.7.3.3 A figure of the Composite Local Skin Reaction score, of the erythema component, and of the edema component by visit and by treatment group will be generated.
- 5.6.7.4 The incidence of AEs and TEAEs, as well as the intensity and relationship to study drug will be summarized by treatment group.
- 5.6.7.5 Safety will also be assessed by evaluating findings of physical examinations, vital signs, clinical laboratory test results, 12-lead ECG tracings, concomitant medications, and withdrawals/terminations/drug holiday/dosing adjustment by treatment group.
- 5.6.7.6 ECG data will be derived from 12-lead ECG tracings (and from cardiac Holter monitoring recordings, if appropriate).
- 5.6.7.7 Summary statistics for observed measures and changes from pre-dose in the following ECG variables will be tabulated at each post-baseline visit:
  - 5.6.7.7.1 Heart rate (bpm)
  - 5.6.7.7.2 PR interval (ms)
  - 5.6.7.7.3 QRS complex (ms)
  - 5.6.7.7.4 QT interval (ms)

	DOCUMENT NUMBER: 029-BST-PLN-001	PAGE: 34 of 45
TITLE: Statistical Analysis Plan for study: A Phase 2 Randomized, Double-Blind, Placebo-Controlled, Parallel-Cohort Study to Evaluate the Efficacy, Safety, Tolerability, and Pharmacokinetics of Once-Daily Application of Topical VDA-1102 Ointment for 28 Days in Subjects with Actinic Keratosis	EFFECTIVE DATE : 22/MAY/2017 REVISION NUMBER : 2.0	

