#### ***Safety Analysis***

The safety end point data will be summarized for the ITT population. AEs will be categorized by System Organ Class (SOC) and Preferred Terms (PT) using the Medical Dictionary for Regulatory Activities (MedDRA) version 19.1 or higher. The incidence of AEs, as well as the intensity and relationship to study drug, will be summarized by treatment group. Safety will also be assessed by evaluating findings of physical examinations, vital signs, Local Skin Reaction Scores, clinical laboratory test results, 12-lead ECG tracings, drug exposure, concomitant medications, and withdrawals/terminations. Clinical and laboratory data will be presented by dose group. Continuous variables will be described as the mean, median, standard deviation, and minimum and maximum values of n observations. Categorical data will be described with contingency tables including frequency and percent. These findings will be

summarized and compared between treatments and within treatment groups compared to findings from baseline evaluations.

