## 15. ADVERSE EVENTS

### 15.1 Adverse Event Definition

An AE is any untoward medical occurrence in a subject administered a pharmaceutical product, which does not necessarily have to have a causal relationship with the pharmaceutical product treatment. Any worsening of the subject's disease under study or other medical conditions will also be considered to be an AE, unless it is within the normal range of disease fluctuation for that subject.

**In this trial LSRs will be collected independently of AEs. Any LSR that occurs within the selected Treatment Field and extends to adjacent surrounding skin (defined as within a 2 cm border around the Treatment Area) will be considered LSRs and will not be recorded as AEs. LSRs that require medical intervention (prescription medication) or extend beyond the 2 cm surrounding skin should be documented as an AE.**

Clinically meaningful (for a given subject) changes in physical examination and test findings should also be recorded as AEs. The criteria for determining whether an abnormal objective test finding should be reported as an AE are as follows:

1. Test result is associated with accompanying symptoms, and/or
2. Test result requires additional diagnostic testing or medical/surgical intervention, and/or
3. Test result leads to a change in study dosing or discontinuation from the study, significant additional concomitant drug treatment, or other therapy, and/or
4. Test result leads to any of the outcomes included in the definition of a SAE.

Merely repeating an abnormal test, in the absence of any of the above conditions, does not meet Condition 2 above for reporting as an AE.

Any abnormal test result that is determined to be an error does not require reporting as an AE.

Treatment Emergent Adverse Events (TEAEs) are AEs that occur *de novo* or worsen following the initiation of study treatment.

Surgical procedures themselves are not AEs; they are therapeutic measures taken for the AE, and should be documented as such.

Planned hospital admissions documented in the subject's CRF prior to randomization and study-related procedures are also not AEs.

Overdoses of the study drug will not be reported as an AE. However, any AEs or SAEs, as defined in Section 15, associated with an overdose will be reported as such.

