### **17.2.2 Safety Assessments**

The safety end point data will be summarized for the ITT population. AEs will be categorized by System Organ Class (SOC) and Preferred Terms (PT) using the Medical Dictionary for Regulatory Activities (MedDRA version 19.1 or higher). The incidence of AEs, as well as the intensity and relationship to study drug will be summarized by treatment group. Safety will also be assessed by evaluating findings of physical examinations, vital signs, dermatologic assessments, clinical laboratory test results, 12-lead ECG tracings, Local Skin Reaction Score, drug exposure, concomitant medications, and withdrawals/terminations. These findings will be summarized and compared between treatments and within treatment group compared to findings from baseline evaluations.

Local Skin Reaction scores (LRS) will be summarized by treatment.

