## 5.6 Statistical Analysis

### 5.6.1 General

5.6.1.1 All measured variables and derived parameters will be listed individually and, if appropriate, tabulated by descriptive statistics. For categorical variables summary tables will be provided giving sample size, absolute and relative frequency and 95% CI (Confidence Interval) for proportions (if appropriate) by treatment group. For continuous variables summary tables will be provided giving sample size, arithmetic mean, standard deviation, coefficient of variation CV% (if appropriate), median, minimum and maximum and 95% CI (Confidence Interval) for means of variables (if appropriate) by treatment group. The data will be analyzed using the SAS ® version 9.3 or higher (SAS Institute, Cary North Carolina). Analyses presented in the clinical report but not mentioned in the SAP are unplanned or ad-hoc analyses.

5.6.1.2 Statistical methods presented in the SAP may be slightly different from those that are presented in the protocol. Differences are clearly stated in this SAP which supersedes the protocol only with regard to the way data will be handled and analysed.

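### The SAP plans only within-arm tests of local skin reaction change and, without saying so, leaves out the between-treatment comparison in protocol 17.2.2

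*SAP*

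**What the plan says.** Protocol 17.2.2 (Safety Assessments) lists the LSR score with physical examination, vital signs, laboratory results, ECG and other findings, and then states: "These findings will be summarized and compared between treatments and within treatment group compared to findings from baseline evaluations". The synopsis gives a similar list, also including LSR, to be "summarized and compared between treatments and within treatment groups compared to findings from baseline evaluations". Protocol 17.2.2 also has a sentence on LSR alone: "Local Skin Reaction scores (LRS) will be summarized by treatment".

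SAP 5.6.7.3.1 names what is analyzed: "The within-group changes from baseline to each visit in the Composite Local Skin Reaction score", and likewise every component, by paired t-test or signed-rank test. SAP 5.6.7.3.2 repeats this in subjects who completed Day 84. SAP 5.6.7.3.3 adds a display: "A figure of the Composite Local Skin Reaction score, of the erythema component, and of the edema component by visit and by treatment group". The general rule in SAP 5.6.1.1 provides a "95% CI (Confidence Interval) for means of variables (if appropriate) by treatment group". LSR is absent from the safety findings that SAP 5.6.7.5 lists for evaluation by treatment group.

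Two general rules bear on this. SAP 5.6.1.2 says that departures from the protocol are stated in the SAP and that the SAP takes precedence on analysis. SAP 5.6.1.1 classes any reported analysis that the SAP does not mention as unplanned or ad hoc.

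Protocol 15.1 keeps reactions in the Treatment Field and its 2 cm border out of adverse event reporting: they "will be considered LSRs and will not be recorded as AEs". The exceptions are reactions that need prescription medication or that spread beyond the border.

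**The concern.** The placebo is the ointment without the active ingredient (protocol 13.1). Daily application of the vehicle may itself irritate or soothe the skin, and LSR scores may also drift over time. A change from baseline inside an active arm mixes all of that with any effect of the drug. Only the contrast with the vehicle arm isolates the drug.

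A within-arm p-value answers whether that arm changed. It does not answer whether the drug changed the skin more than the vehicle did. When three within-arm results stand side by side, a reader is likely to take a significant active arm next to a non-significant placebo arm as a drug effect. That inference has no error control.

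Adverse event tables fill little of the gap, because most reactions in the field are not recorded as adverse events. The LSR score is therefore the main source on local tolerability, which is part of a secondary objective.

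**Working it through.** **1. What carries over from protocol to SAP.** The protocol sentence has two parts, between treatments and within group. SAP 5.6.7.3.1 and 5.6.7.3.2 implement the second. No SAP section names an active-versus-placebo LSR test, difference or interval. Where the SAP wants that contrast it says so: 5.6.5.2 (Day 56 lesion count), 5.6.6.4 (clearance) and 5.6.6.8 (Day 84 count) each set every active group against placebo. Nothing in the SAP declares the LSR omission as a departure.

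**2. Number of tests.** There are nine components plus the composite (protocol 22.1), six post-baseline visits (Days 7, 14, 28, 35, 56 and 84; protocol Table 5) and three arms: 10 × 6 × 3 = 180 within-arm tests, before the repeat in Day 84 completers. No between-arm test is named. This count describes the plan; it does not measure harm.

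**3. The plan's own figure.** The documents give no sample size or power for LSR. For the primary endpoint (25 per arm, effect size 0.83, two-sided 0.045) the stated power is 80%. The noncentral t calculation on 48 degrees of freedom gives 80.7%, so the figure reproduces.

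**4. How often within-arm tests disagree when the drug adds nothing.** Assume the same true standardized change d in all three arms, two-sided alpha 0.05 and independent arms. Let p be the power of the paired t-test at n per arm (noncentral t, n − 1 degrees of freedom, noncentrality d√n).

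- A given dose is significant and placebo is not: p(1 − p).
- At least one of the two doses is significant and placebo is not: (1 − (1 − p)²)(1 − p).

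Example at n = 28, d = 0.4: p = 0.532. One dose: 0.532 × 0.468 = 0.249. Either dose: (1 − 0.468²) × 0.468 = 0.781 × 0.468 = 0.365.

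| Assumed d (SD) | p, n = 28 | One given dose | Either dose, n = 28 | Either dose, n = 25 |
|---|---|---|---|---|
| 0.1 | 0.080 | 7% | 14% | 14% |
| 0.2 | 0.175 | 14% | 26% | 25% |
| 0.3 | 0.334 | 22% | 37% | 36% |
| 0.4 | 0.532 | 25% | 37% | 38% |
| 0.5 | 0.723 | 20% | 26% | 29% |
| 0.6 | 0.864 | 12% | 13% | 17% |
| 0.8 | 0.983 | 2% | 2% | 3% |

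The either-dose probability cannot exceed 38.5%, whatever d is. A direct between-arm test would hold the error at 5% per comparison.

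**5. What the added comparison would deliver.** The half-width of a 95% CI for a dose-minus-placebo difference, in SD units, is t(0.975, 2n − 2) × √(2/n).

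- n = 28: 2.005 × 0.2673 = 0.54 SD
- n = 25: 2.011 × 0.2828 = 0.57 SD

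A two-sided 0.05 test reaches 80% power at a true difference of 0.76 SD (n = 28) or 0.81 SD (n = 25).

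**The case against.** The strongest reply is that nothing is lost. The trial has a randomized, blinded vehicle arm, and LSR is scored at baseline and every later visit (protocol 10.1.5). The SAP plans figures by arm, LSR tables (14.3.5-14 to 14.3.5-17) and per-arm means with intervals where appropriate, so a reader can form the difference. The protocol's word for comparison names no test or estimate, its LSR-specific sentence asks only for a summary by treatment, and the SAP meets that. Testing only within group is also this SAP's convention for vital signs, ECG and laboratory data (5.6.7.10).

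Much of this stands, and it limits the point in several ways. A reader might infer that the trial cannot separate drug irritation from vehicle irritation; the design and data show that it can. A reader might infer that the protocol promised a formal between-arm LSR test; it did not, and side-by-side description is a possible reading. A reader might infer that tolerability against placebo is itself the secondary objective. The objective is to evaluate tolerability under each treatment, placebo included, whereas the primary and exploratory objectives speak of comparing. Nor would a drug-minus-vehicle contrast test the advantage claimed in protocol 5.3, which is over existing field treatments. The table shells are available by title only, so the absence of a between-arm test is established for the SAP text and not for the shells.

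The disagreement rates also do harm only if someone reads across the arms' p-values, and the SAP plans no such inference.

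What does not stand is that the by-arm material makes the difference a planned result. Three separate means and three within-arm p-values give neither a dose-minus-placebo estimate nor its interval. The same convention for other safety data does not excuse LSR, which adverse event reporting largely leaves out.

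**Conclusion.** The point holds as a gap in pre-specification, not in the design. The only LSR inference in the SAP text is within arm. The between-treatment comparison in protocol 17.2.2 and the synopsis is not carried over, and the omission is undeclared although SAP 5.6.1.2 says that differences are stated. A drug-versus-vehicle LSR comparison produced later would carry the ad hoc label.

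The size depends on an LSR change that the documents do not give. With equal true change in all arms, the misleading pattern for at least one dose is common for assumed changes of 0.2 to 0.5 SD, less so at 0.1 or 0.6 SD, and rare at 0.8 SD. These rates rest on 28 per arm, a two-sided 0.05 level (also not stated for LSR) and independent arms, and apply to one score at one visit. The change should be made because it is cheap and answers the question that the vehicle arm is there to answer.

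**What to change.** In SAP 5.6.7.3 add, for each dose versus placebo, the difference in composite LSR change from baseline at the on-treatment visits (Days 7, 14 and 28) with a 95% CI. Adjust for the baseline score, or use a rank-based estimate such as Hodges-Lehmann if the scores are skewed. Present the components by arm without testing, and label the within-arm p-values descriptive. A comparison of the maximum on-treatment score is optional. If the sponsor prefers to keep LSR descriptive, the SAP should state and justify that departure from protocol 17.2.2.

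The cost is SAP wording and one extra table, with no new data or subjects. The downside is wide intervals, about 0.54 to 0.57 SD either side, so an unremarkable result should not be reported as equivalence to vehicle.
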